8.3.7 REPORTING EVENTS TO PARTICIPANTS

All SAEs judged to be possibly, probably, or definitely related to the investigational product(s) will be reported to study participants via group meetings and/or one-on-one sessions with a study clinician and/or modifications or supplements to the informed consent form. Every effort will be made to maintain the confidentiality of the affected participant(s) while still providing enough information to other participants to allow them to fully assess the risks of continued involvement in the study. Informed consent forms will be updated with information concerning all SAEs judged to be possibly, probably, or definitely related to the investigational products, and participants.

8.3.8 EVENTS OF SPECIAL INTEREST

Not applicable.

8.3.9 REPORTING OF PREGNANCY

Each pregnancy must be reported **within 72 hours of identification** by email or fax to Sanaria and to the clinical center IRB in accordance with IRB policy.

Participants who become pregnant after Day 1 will be followed to term, and the following information will be gathered for outcome: date of delivery, health status of the mother and child including the child's gender, height and weight. Complications and or abnormalities should be reported including any premature terminations. A pregnancy is reported as an AE or SAE only when there is suspicion that the investigational product may have interfered with the effectiveness of contraception or there was a serious complication in the pregnancy including a spontaneous abortion or an elective termination for medical rationale.

8.4 UNANTICIPATED PROBLEMS

8.4.1 DEFINITION OF UNANTICIPATED PROBLEM INVOLVING RISKS TO PARTICIPANTS OR OTHERS (UPIRTSO)

An Unanticipated Problem Involving Risks to Subjects or Others (UPIRTSO) is defined as involving risks to participants or others to include, in general, any incident, experience, or outcome that meets **all** of the following criteria:

- Unexpected in terms of nature, severity, or frequency given (a) the research procedures that are described in the research protocol and informed consent document; and (b) the characteristics of the participant population being studied;
- At least possibly related to participation in the research; and
- Suggesting that the research places participants or others at a greater risk of harm (including physical, psychological, economic, or social harm) than was previously recognized.

8.4.2 UNANTICIPATED PROBLEM REPORTING

The investigator will report unanticipated problems (UPs) to the reviewing IRBs, HRPO and to the Sponsor. The UP report will include the following information:

- Protocol identifying information: protocol title and number, PI's name, and the IRB project number;
- A detailed description of the event, incident, experience, or outcome;
- An explanation of the basis for determining that the event, incident, experience, or outcome represents a UP;
- A description of any changes to the protocol or other corrective actions that have been taken or are proposed in response to the UP.

To satisfy the requirement for prompt reporting, UPs will be reported as follows:

- UPs that are SAEs will be reported as SAEs.
- Unanticipated Problems Involving Risk to Subjects or Others (UPIRTSOs) will be reported to the Sponsor within 48 hours and a written report will follow within 10 days.
- Any other UP will be reported to the IRB (excepting IRBs providing administrative review) and to the Sponsor within 7 days of the investigator becoming aware of the problem.
- All UPs should be reported to regulatory institutions as required by an institution's written reporting procedures.

The Sponsor may also be the source of the UP report (e.g., failure of sterility testing in the vaccine lot). The Sponsor will report UPs relevant to participant safety to the SMC, and may schedule a SMC meeting to review, if appropriate. In addition, the Sponsor will notify the FDA and all participating investigators of potential significant risks represented by a UP, and this will be done no later than 15 calendar days after the Sponsor determines that the information qualifies for reporting. Other UPs (not posing a significant risk) will be reported by the Sponsor to the SMC in periodic reports and to FDA in the annual report to the IND.

8.4.3 REPORTING OF UNANTICIPATED PROBLEMS TO PARTICIPANTS

All UPs, if they directly affect the safety risk of study participants, will be reported to study participants via group meetings and/or one-on-one sessions with a study clinician and/or modifications or supplements to the informed consent forms. Every effort will be made to maintain the confidentiality of the affected participant(s) while still providing enough information to other participants to allow them to fully assess the risks of continued involvement in the study. Informed consent forms will be updated with information concerning all such UPs, and participants will be asked to sign the updated ICF if they agree to continued involvement in the study.

9. STATISTICAL CONSIDERATIONS

9.1 STATISTICAL HYPOTHESES FOR PRIMARY ENDPOINTS

9.1.1 PRIMARY ENDPOINTS

VE computed as one minus the estimated risk ratio for Pf infection (parasitemia) detected by PCR beginning 7 days after CHMI and censoring participants at 28 days in the “modified intention to treat” (mITT) population. The mITT population includes any participant completing all 3 doses and CHMI and receiving at least 20% of the injectate IV with each dose (see below).

Null hypothesis: there will be no significant difference between the vaccine group and the control group with regard to proportion protected (no parasitemia) and any observed difference is due to sampling or experimental error.

Alternative hypothesis: a statistically significant difference exists between the vaccine group and the control group with regard to proportion protected (no parasitemia).

The sample size for this study was not designed to test a formal hypothesis concerning vaccine safety

9.2 SAMPLE SIZE DETERMINATION

The primary outcome for these studies will be VE measured as $[1 - \text{risk ratio}] \times 100$. The outcomes of both CHMI's will be combined. Sample sizes of 45 and 15 for the vaccine and placebo groups were selected to be able to show with 83% power, if there are six drop-outs from the vaccine group and two from the control group prior to CHMI, that an infection rate of 92.3% in the controls (12/13 developing parasitemia) and 51% in the vaccinees (20/39 developing parasitemia) is statistically significantly different ($\alpha=0.05$, 2-tailed) (VE=44.4%). As we expect VE to be higher than this, the sample size should be adequate.

Regarding safety, the study provides the following power to identify adverse outcomes:

1. If no PfSPZ Vaccine-related SAEs are observed, the sample size of 45 provides 95% confidence that the true rate of SAEs caused by immunization is less than 6.7%, 90% confidence that the true rate of SAE's is less than 5.0%, 85% confidence that the true rate of SAEs is less than 4.2%, and 80% confidence that the true rate of SAEs is less than 3.5%.
2. With regard to the ability to make comparisons between vaccinees and placebo recipients in the rates of grade 2 and grade 3 adverse events, where significant differences might indicate poor tolerability, a sample size of 45 vaccinees and 15 placebo recipients will show a statistically significant difference ($p<0.05$, two-tailed) between 10/45 vaccinees experiencing poor tolerability on the one hand, and 0/15 controls on the other hand.

Immunogenicity:

Antibody responses (group means, standard deviations, medians and ranges) will be used to compare participants with controls, and to compare infected and non-infected participants, the latter to look for trends suggesting a threshold response above which VE is seen, using appropriate nonparametric tests such as Wilcoxon and Spearman correlation. The data management vendor is providing biostatistical consultation and will generate the Statistical Analysis Plan, which will be finalized in advance of the database lock. The same vendor will conduct the statistical analyses.

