1. VE computed as one minus the estimated risk ratio for Pf malaria (parasitemia) detected by PCR beginning 7 days after CHMI up to 28 days in the modified intention to treat population (proportional efficacy analysis) combining data across the two CHMI timepoints.
2. The differences in proportions of vaccinees compared to controls experiencing related moderate, severe, or serious solicited and unsolicited adverse events and laboratory abnormalities after vaccination.

Secondary Endpoints

1. VE as above, for each timepoint.
2. Antibody levels to PfCSP measured by ELISA comparing vaccinees to controls, and protected (no parasitemia occurring post CHMI) to non-protected (parasitemia occurring post CHMI) vaccinees.

Exploratory Endpoints:

1. VE as above.
2. VE as above.
3. VE computed as one minus the estimated hazard ratio.
4. Investigation of any differences in outcome based on gender, race or ethnicity.
5. Antibody levels to whole PfSPZ by automated immunofluorescence assay (IFA) and/or by other assays to be further defined, which may include assays to assess responses to multiple Pf antigens, antibody subclass assays and functional assays, comparing vaccinees to controls, and protected (no parasitemia occurring post CHMI) to non-protected (parasitemia occurring post CHMI) vaccinees.
6. Capacity to inhibit sporozoite invasion of hepatocytes (HC-04 cells) in vitro by inhibition of sporozoite invasion (ISI) assay comparing vaccinees to controls, and protected (no parasitemia occurring post CHMI) to non-protected (parasitemia occurring post CHMI) vaccinees.
7. Cellular immune responses to whole PfSPZ and synthetic peptides from selected Pf antigens by intracellular cytokine staining (ICS)/ flow cytometry and/or other assays to be defined comparing vaccinees to controls, and protected (no parasitemia occurring post CHMI) to non-protected (parasitemia occurring post CHMI) vaccinees.
8. RNA transcriptome quantification as detected by RNA-seq and protein levels in serum, and serum analyte analysis, comparing vaccinees to controls, and protected (no parasitemia occurring post CHMI) to non-protected (parasitemia occurring post CHMI) vaccinees.
9. Deep sequencing of immune receptor genes.

Methodology

This will be a randomized, double-blind, placebo-controlled trial conducted at a single site as described above. Participants will be randomized to PfSPZ Vaccine

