2.2.1.1.3 META-ANALYSIS OF ADULT AND PEDIATRIC SAFETY

A meta-analysis of AE data is shown for adults and children using forest plots of total solicited AEs in vaccinees and placebos in the randomized, double-blind, placebo-controlled trials analyzed to date (**Figure 2**). In all cases, 95% confidence intervals cross a ratio of 1, indicating no differences between vaccinees and controls.

Figure 2. Effect of Vaccine on Incidence of any Solicited Systemic Adverse Event (AE) per Study Participant in Randomized, Double-Blind, Placebo-Controlled Trials of PfSPZ Vaccine in Adults Age ≥ 18 Years in Sub-Saharan Africa

[figure not shown]

#Vac. is the number of participants enrolled in the vaccine arm in each study; # Plac. is the number of participants enrolled in the NS control arm of each study.

Numbers in parentheses are the number of participants experiencing any solicited adverse event (AE) after any of the injections administered. Solicited local AEs were collected for three days (BSPZV2, BSPZV3, EGSPZV2 and EGSPZV3) or seven days (BSPZV1, EGSPZV1, BFSPZV1 (DMID protocol ID 15-0001), MLSPZV1 and MLSPZV2 (DMID protocol ID 16-I-N004)) after each dose, while solicited systemic AEs were collected for seven days after each dose, except for MLSPZV1, for which they were collected for 28 days after each dose. Depending on the trial, solicited local AEs included pain, tenderness, erythema, swelling, induration and pruritus; solicited systemic AEs included fever (measured), fever (subjective), headache, fatigue/malaise, arthralgia, myalgia, rash/pruritus/urticaria, chills/rigors, nausea/vomiting, abdominal pain, diarrhea, chest pain, palpitations, shortness of breath, bradycardia/tachycardia, hypertension/hypotension.

Figure 3. Effect of vaccine on incidence of any solicited systemic adverse events per study participant in randomized, double-blind, placebo-controlled trials of PfSPZ Vaccine in infants and children aged 5 months to <18 years in sub-Saharan Africa.

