9.4.4 ANALYSIS OF SAFETY

The inclusion of randomized, blinded normal saline controls allows unbiased collection of AE data. Because normal saline is physiologically inert, the rate of AEs recorded in normal saline recipients will represent background rates in the population. The use of any vaccine comparator other than normal saline would make it impossible to measure AEs due to PfSPZ Vaccine because these would be obscured by AEs caused by the comparator vaccine.

AEs and laboratory abnormalities will be analyzed based on the safety cohort dataset. Solicited local and systemic adverse events will be assessed individually and as total local or systemic adverse events. Unsolicited adverse events will be classified by the Medical Dictionary for Regulatory Activities (MedDRA) at the preferred term level and also will be assessed individually and as total unsolicited adverse events. The overall percentage of participants with a solicited local adverse event, a solicited systemic adverse event, an unsolicited adverse event, a laboratory abnormality or an SAE during the appropriate surveillance periods after immunization will be tabulated. The severity and relationship to study product will be tabulated as well. Rates of adverse events will be compared between vaccine and control groups and compared statistically using Fisher's exact test. In addition, laboratory abnormalities deemed clinically relevant will be tabulated by study group and rates of occurrence compared between vaccinees and controls.

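### The tolerability endpoint is a difference in proportions, but the plan gives that difference no confidence interval, and a non-significant Fisher test on 45 v 15 could not support a claim of no difference from saline.

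*Combined protocol and SAP*

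**What the plan says.** The synopsis (1.1) defines the second primary endpoint as "The differences in proportions of vaccinees compared to controls experiencing related moderate, severe, or serious solicited and unsolicited adverse events", together with laboratory abnormalities. Section 3.2 gives the same endpoint without the severity limit. Both define it as a difference in proportions, and neither names an interval.

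Section 9.2, safety item 1, handles SAEs by an upper confidence limit when no event is seen. Item 2 handles tolerability by significance. It speaks of comparisons "in the rates of grade 2 and grade 3 adverse events, where significant differences might indicate poor tolerability". As its one example, it claims that the planned arm sizes would reach two-sided significance at the 0.05 level "between 10/45 vaccinees experiencing poor tolerability on the one hand, and 0/15 controls on the other hand".

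Section 9.4.4 plans to tabulate percentages, severity and relatedness, and then: "Rates of adverse events will be compared between vaccine and control groups and compared statistically using Fisher's exact test". Section 9.1.1 adds: "The sample size for this study was not designed to test a formal hypothesis concerning vaccine safety". The Statistical Analysis Plan is to be written later (9.2, 9.4.1).

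**The concern.** The endpoint is an estimate, but the only inferential output planned for it is a p-value. A p-value from 15 controls does not tell the reader how large an excess of grade 2 or 3 events the data still allow. For SAEs the plan does say this; for tolerability it does not.

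The background shows how a null comparison can come to be read. Of the pooled earlier trials, section 2.2.1.1.3 says that "95% confidence intervals cross a ratio of 1, indicating no differences between vaccinees and controls". Section 2.2.1.1.2 likewise uses the lack of significant differences in earlier trials to doubt whether the vaccine has consistently caused any adverse reaction. The same section calls the adverse event profile of condensed regimens not fully resolved, and this trial uses a condensed regimen. An estimate of the possible excess is therefore what the trial should supply. If this trial's result were read in the same way, a primary conclusion would rest on a test with little ability to contradict it.

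**Working it through.** **Inputs.** 45 vaccinees and 15 controls, alpha 0.05 two-tailed (9.2). Fisher's exact test (9.4.4). No dropout adjustment, because the safety cohort is everyone dosed at least once (9.3.2). The control rate of grade 2-3 events is not given, so 0% to 40% is assumed.

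**Step 1: the plan's own example, 10/45 v 0/15.** With 10 events among 60 people, the chance that none falls among the 15 controls is C(45,10)/C(60,10) = 0.0423. The two-sided Fisher test adds every table no more likely than this one. These are the tables with 6 or more of the 10 events among controls: 0.0099 + 0.0012 + 0.0001 = 0.0112. The total is 0.0535, so the example is not significant at 0.05.

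| Vaccine v control | Two-sided Fisher p |
|---|---|
| 10/45 v 0/15 | 0.0535 |
| 11/45 v 0/15 | 0.0505 |
| 12/45 v 0/15 | 0.0269 |

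The uncorrected chi-square for 10/45 v 0/15 is 60 × (10×15 − 35×0)² / (45×15×10×50) = 4.00, p=0.0455. The stated figure may therefore have come from a different test than the one planned.

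**Step 2: power for a true 20-point excess.** Power is the sum, over all 46 × 16 possible tables, of Bin(a; 45, pC+0.20) × Bin(b; 15, pC), counting tables with two-sided Fisher p<0.05 and the higher rate in the vaccine arm. At pC=0 this is P(X ≥ 12) for X ~ Bin(45, 0.20), which is 0.174.

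| Assumed control rate | Vaccine rate | Power | Missed |
|---|---|---|---|
| 0% | 20% | 17% | 83% |
| 5% | 25% | 26% | 74% |
| 10% | 30% | 29% | 71% |
| 15% | 35% | 27% | 73% |
| 20% | 40% | 24% | 76% |
| 30% | 50% | 22% | 78% |
| 40% | 60% | 21% | 79% |

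For 80% power the excess must be about 32 points (control 0%), 35 (5%), 39 (10%) or 43 (20% to 30%). The more liberal uncorrected chi-square has exact power of only 27% to 41% for a 20-point excess.

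**Step 3: what an interval would show.** The Newcombe interval combines the Wilson limits (l, u) of each arm:
lower = d − √[(p1 − l1)² + (u2 − p2)²]; upper = d + √[(u1 − p1)² + (p2 − l2)²].

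For 9/45 v 0/15 the Wilson limits are 0.1090 to 0.3382 and 0 to 0.2039. Lower = 0.200 − √(0.0910² + 0.2039²) = −0.023. Upper = 0.200 + 0.1382 = 0.338.

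| Observed | Difference | 95% Newcombe interval (points) | Fisher p |
|---|---|---|---|
| 9/45 v 0/15 | 20 | −2.3 to +33.8 | 0.096 |
| 12/45 v 1/15 | 20 | −5.5 to +35.4 | 0.153 |
| 15/45 v 2/15 | 20 | −7.3 to +37.5 | 0.192 |
| 6/45 v 2/15 | 0 | −25.5 to +16.0 | 1.00 |

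The first three results are non-significant, and each still allows an excess above 30 points. Even with identical observed rates of 13.3%, an excess of 16 points is not excluded.

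**The case against.** A reader might infer that the plan judges tolerability solely by Fisher significance, and that a non-significant result will be reported as good tolerability. The documents do not support that. Section 9.2 says only that a significant difference might point to poor tolerability and is silent on a non-significant one. Section 9.1.1 disclaims a safety hypothesis. The passage in 2.2.1.1.3 is background on earlier trials, not an analysis rule for this one.

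Nor is the p-value the only safeguard. Under 7.2, three vaccinees with the same related grade 3 event, or the same grade 3 laboratory abnormality, or one vaccinee with a related SAE, trigger review by the Safety Monitoring Committee. The study can also be paused on lesser patterns. The committee sees the safety data again at the end (10.1.8). If, as an assumption, 10% of vaccinees had the same related grade 3 event, the three-case rule would trigger with probability 1 − (0.009 + 0.044 + 0.107) = 84%. Fisher power is therefore not the trial's whole sensitivity to harm.

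Low power for adverse event comparisons is also inherent in 60 participants, and an interval does not change it. The later SAP could add one.

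All of this stands, and it limits the point to estimation and reporting. The pausing rules protect participants but do not estimate an excess, and their specified triggers do not count grade 2 events that are not serious. Percentages without an interval do not show what excess remains possible. Nothing in the supplied text commits the SAP to an interval.

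**Conclusion.** The point holds as a gap in the analysis of a primary endpoint. No interval is specified for the difference in proportions, and the planned Fisher test would miss a true 20-point excess 71% to 83% of the time. The control rates are assumptions, but power stays below 30% at every rate examined from 0% to 40%. A non-significant result therefore could not carry a conclusion of similarity to saline. Whether such a conclusion would be drawn is not settled by the plan; the background only makes it plausible.

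Separately, and with no assumption about rates, the example in 9.2 item 2 is wrong under the test named in 9.4.4.

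**What to change.** In 9.4.4, or in the SAP before database lock:
- Report the risk difference (vaccine minus saline) with a two-sided 95% Newcombe or Miettinen-Nurminen interval, for any related event of grade 2 or higher and for each main class (local, systemic, unsolicited, laboratory).
- State the upper limit as the largest excess that the data do not exclude.
- Keep Fisher p-values as descriptive, and say that a non-significant one will not be reported as absence of a difference. The two can disagree at the margin: 11/45 v 0/15 has p=0.0505 but a Newcombe interval of +1.6 to +38.7 points. The text should therefore say that the interval leads.

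In 9.2 item 2, replace 10/45 with 12/45 (p=0.027), or name the test that was used, and add the power for a 20-point excess.

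The cost is wording and one extra column in the adverse event tables, with no added participants. The downside is that wide upper limits will make the safety statement less favourable.

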(vaccinees) or normal saline (NS) placebo (controls) in a 3:1 assignment ratio. PfSPZ Vaccine and NS injectates are prepared as clear, non-viscous, odor-free solutions that cannot be distinguished by the administrator or by the recipient, facilitating a double-blind design. Randomization will be done online using software provided by data management.

There will be 45 vaccinees and 15 controls. The reasons for the 3:1 imbalance are to: 1) collect more information on adverse events associated with vaccine administration, and 2) optimize the numbers to assess vaccine efficacy (VE) in the CHMI model. Participants who complete all immunizations will receive a total of 2.7×10^6 PfSPZ. In prior studies, single doses of 2.7×10^6 PfSPZ have been well tolerated in non-immune adults and there has not been any evidence that repeat dosing leads to increasing side effects. Therefore, 3 doses of 9.0×10^5 PfSPZ has been shown to be very safe and well tolerated.

Table 1. USSPZV7 Study Design

Groups	n	PfSPZ Vaccine dose (# PfSPZ)	Total PfSPZ over 3 doses (# PfSPZ)	Immunization (Days)			Weeks to CHMI	PfSPZ Challenge (7G8) dose (# PfSPZ)
				1	8	29		
1 -PfSPZ Vaccine	45	9.0×10^5	2.7×10^6	x	x	x	x	3.2×10^3
2 -NS* controls	15	0	0	x	x	x	x	3.2×10^3
Total # of participants: 60								

* normal saline placebo

VE will be assessed 3 and 12 weeks after last immunization by exposure to PfSPZ Challenge (7G8), which is composed of aseptic, purified, cryopreserved infectious PfSPZ cloned from a Pf strain isolated in Brazil, and thus heterologous to the vaccine, which is derived from strain PfNF54 originating in West Africa. As with immunization, the PfSPZ will be administered by direct venous inoculation (DVI). Participants will be followed intensively for 4 weeks after CHMI to determine CHMI outcome and then for an additional 4 weeks until last study visit. Parasitemia following CHMI will be measured by highly sensitive quantitative polymerase chain reaction (qPCR). Protection will be defined as absence of parasitemia as detected by qPCR during the 28 days following injection of 3.2×10^3 PfSPZ of PfSPZ Challenge (7G8).

Statistical Methods

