9.3.2 SAFETY COHORT

The safety cohort is a subset of the total cohort and will include all participants receiving at least one immunization. Participants will be analyzed according to immunization received. Participants who have received at least one immunization will not be excluded from the safety population for ineligibility, missing follow-up immunization, or protocol deviations.

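### The safety illustration of 10/45 versus 0/15 is not significant under the Fisher's exact test planned in 9.4.4 (p=0.0535); the smallest significant count is 12/45

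*Combined protocol and SAP*

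**What the plan says.** Section 9.2 (safety, item 2) deals with comparing "rates of grade 2 and grade 3 adverse events, where significant differences might indicate poor tolerability". It says that the planned groups, 45 on vaccine and 15 on placebo, "will show a statistically significant difference ($p<0.05$, two-tailed"). The observed table to which this claim is attached is the contrast "between 10/45 vaccinees experiencing poor tolerability on the one hand, and 0/15 controls on the other hand". The synopsis carries the same sentence under its statistical methods. Neither place names the test behind the figure.

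Section 9.4.4 does name one: "Rates of adverse events will be compared between vaccine and control groups and compared statistically using Fisher's exact test". It does not give the sidedness.

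Two other statements bear on the point. The safety cohort in 9.3.2 "will include all participants receiving at least one immunization", so no drop-out allowance comes off the denominators. And 9.1.1 closes with: "The sample size for this study was not designed to test a formal hypothesis concerning vaccine safety".

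**The concern.** A reader who combines the two-tailed 5% level of 9.2 with the test of 9.4.4 will expect 10/45 against 0/15 to be significant, and it is not.

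Safety and tolerability is the second primary objective, and its endpoint is a difference in proportions between vaccinees and controls. Item 2 of 9.2 is the only place where the plan says what that comparison could show; item 1 concerns SAEs in vaccinees alone. If exactly this table, or 11/45 against 0/15, were observed, the protocol would have called 10/45 significant in advance while the planned analysis reported a p-value above 0.05. It would then be awkward, after unblinding, to explain which statement governs.

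**Working it through.** **Inputs**
- Group sizes 45 and 15: "There will be 45 vaccinees and 15 controls" (1.1), with the full denominators kept by the safety cohort definition (9.3.2).
- Level: 0.05, two-tailed (9.2).
- Test: Fisher's exact (9.4.4), taken as two-sided because 9.2 says two-tailed.
- Table claimed to be significant: 10/45 (22.2%) against 0/15.

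**Trying to reproduce the plan's figure**

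Uncorrected Pearson chi-square for x/45 against 0/15 is 60 × (15x)² / [45 × 15 × x × (60 − x)].
- x=10: 60 × 22,500 / (45 × 15 × 10 × 50) = 1,350,000 / 337,500 = 4.00, p=0.0455.
- x=9: 60 × 18,225 / (45 × 15 × 9 × 51) = 1,093,500 / 309,825 = 3.53, p=0.0603.

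So 10 is exactly the smallest significant count under this test. That makes it a plausible source of the printed figure, although the documents do not say so. The smallest expected cell is 15 × 10/60 = 2.5, a weak basis for the chi-square approximation.

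**Under the planned test**

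With x events in total, the number k falling in the vaccine group is hypergeometric: P(k) = C(45,k) × C(15,x−k) / C(60,x). The observed table has k=x. The two-sided p-value adds the probabilities of all tables no more likely than the observed one.

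*x=10*
- Observed: C(45,10)/C(60,10) = 0.04231. This is the one-sided p-value.
- Opposite tail: k=4 gives 0.00989, k=3 gives 0.00121, k=2 gives 0.00008, and smaller k are negligible; together 0.0112. The table k=5 (0.04866) is more likely than the observed one and is left out.
- Two-sided p = 0.0423 + 0.0112 = **0.0535**.

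*x=11*
- Observed: 0.02962. Opposite tail, k≤5: 0.01784 + 0.00280 + 0.00027 + 0.00001 = 0.0209.
- Two-sided p = **0.0505**.

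*x=12*
- Observed: 0.02055. Opposite tail, k≤5: 0.00562 + 0.00069 + 0.00005 = 0.0064. The table k=6 (0.02913) is left out.
- Two-sided p = **0.0269**.

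| Vaccinees with event, against 0/15 | Two-sided Fisher p | Uncorrected chi-square p |
|---|---|---|
| 9/45 (20.0%) | 0.0955 | 0.0603 |
| 10/45 (22.2%) | 0.0535 | 0.0455 |
| 11/45 (24.4%) | 0.0505 | 0.0341 |
| 12/45 (26.7%) | 0.0269 | 0.0253 |

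The stated table and the next one both miss 0.05. The first to reach it is 12/45.

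**The case against.** Section 9.2 names no test, and 9.4.4 neither gives a sidedness nor mentions the 10/45 figure, so the two-sided Fisher test is put together from two places. The sentence in 9.2 is true, two-tailed, under an uncorrected chi-square (0.0455) and under Barnard's test with the group sizes held at 45 and 15 (0.0491). This explains how the figure may have arisen but does not rescue it. The chi-square is not the test named for adverse event rates, and Barnard's test is planned in 9.4.3 only for comparing the 3-week and 12-week CHMI cohorts.

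The objection on importance stands. The protocol disclaims a formal safety hypothesis in 9.1.1, and the first paragraph of 9.2 derives 45 and 15 from the efficacy comparison. The safety endpoint has no significance criterion for success. The pausing rules in 7.2 run on event counts, not p-values, and 9.4.4 tabulates severity and relationship whatever the test shows.

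A reader might infer more: that a true excess of 22% over 0% would be reported as not significant, or that the trial's detectable excess is really 26.7%. The documents support neither. The sentence in 9.2 gives an observed-count threshold, not a true rate or a power. If the true rates were 22.2% and 0%, the chance of seeing at least 12 events in 45 is about 29%, and of seeing at least 10 about 56%. So even at the printed threshold, a real excess of that size would be found only a little more often than not, and the protocol does not claim otherwise.

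**Conclusion.** The stated limit and the planned test do not match. With a two-sided Fisher's exact test, 10/45 against 0/15 gives p=0.0535 and 11/45 gives p=0.0505; 12/45 (26.7%, p=0.027) is the smallest observed count that is significant. The shift is two vaccinees, or 4.4 percentage points (26.7% − 22.2%, from 2/45), and the stated table misses 0.05 by 0.0035.

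This rests on three assumptions: the two-tailed level of 9.2 applies to the test in 9.4.4; the denominators are the full 45 and 15; and the two-sided p-value is formed in the usual way, by summing tables no more probable than the observed one. Doubling the one-sided value instead would give 0.0846 at 10/45, 0.0592 at 11/45 and 0.0411 at 12/45, so the threshold of 12 does not depend on that choice.

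The consequence is modest. Sample size, trial conduct and the efficacy analysis are unaffected. What needs correcting is one numerical statement, printed twice, that the planned analysis would contradict.

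**What to change.** In 1.1 and 9.2, replace 10/45 with 12/45 and name the test, for example: 12/45 against 0/15, two-sided Fisher's exact test, p=0.027. Keep Fisher's exact test in 9.4.4 and add there that it is two-sided. Make the change before the SAP is finalised and before unblinding.

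Changing the test in 9.4.4 to one under which 10/45 qualifies is not recommended: it would choose the analysis to preserve an illustrative number, and with Barnard's test only at p=0.049.

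The cost is one figure and a test name in two places, and one word in 9.4.4. The downside is that the stated sensitivity becomes slightly less favourable.
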